5.3 OTHER DATA

The following data also will be collected:

- EQ-5D Quality of Life questionnaire at baseline, 3-months and 1-year only,
- Blood data (White Blood Cell Count, Red Blood Cell Count, Hemoglobin, Hematocrit, Haptoglobin, Reticulocytes, Platelet Count, Serum Lactate Dehydrogenase) at baseline, 3-months, 1- and 5-years only,
- New onset or worsening of conduction disturbances.

6 SUBJECT POPULATION

6.1 DEMOGRAPHIC AND CLINICAL CHARACTERISTICS

Adult male and female subjects diagnosed with aortic stenosis or stenosis-insufficiency and scheduled to undergo aortic valve replacement are eligible for participation in the clinical investigation.

6.2 PRE-OPERATIVE CRITERIA

6.2.1 INCLUSION CRITERIA

The principal investigator at the investigational center has the responsibility of screening potential subjects to determine if the subjects meet all the inclusion criteria. The following are requirements for entry into Phase I or Phase II of the clinical investigation:

- 1. Subject is 18 years or older
- 2. Subject has a ortic stenosis or stenosis-insufficiency of an aortic valve requiring a planned replacement as indicated in the preoperative evaluation.

- 3. Subject is scheduled to undergo planned aortic valve replacement with or without concomitant coronary bypass surgery, MAZE procedure, septal myectomy, pacemaker/ICD implant and or atrial appendage occlusion/removal.
- 4. Subject has signed and dated the investigation informed consent form prior to investigation procedures.
- 5. Subject is geographically stable and agrees to attend follow-up assessments at the hospital of surgical services for a maximum of 5 years.

6.2.2 EXCLUSION CRITERIA

The principal investigator at the investigational center must exclude subjects if any of the exclusion criteria is present. The following are the criteria for exclusion from participating in Phase I or Phase II of the clinical investigation:

- 1. Subject with pure aortic insufficiency.
- 2. Subject requires emergency surgery.
- 3. Subject with an aneurysm of the aortic root and / or ascending aorta requiring surgical intervention).
- 4. Subject with a left ventricular ejection fraction of \leq 25%.
- 5. Subject with a congenital bicuspid or unicuspid aortic valve.
- 6. Subject had active endocarditis within 3 months prior to the scheduled aortic valve replacement surgery.
- 7. Subject with concomitant valve (mitral, tricuspid, or pulmonic) disease requiring repair with an annuloplasty ring or replacement with prosthesis.
- 8. Subject had prior mitral, tricuspid or pulmonic valve surgery, which included implantation of a bioprosthetic valve, mechanical valve, or annuloplasty ring that will remain *in situ*.
- 9. Subject had a myocardial infarction within 1 month prior to the scheduled aortic valve replacement surgery.
- 10. Subject has a disease limiting life expectancy to less than 12 months.
- 11. Subject was previously implanted with EDWARDS INTUITY Aortic Valve⁶.
- 12. Subject is an alcohol and/or drug abuser.
- 13. Female subject is pregnant or lactating.
- 14. Subject is currently participating in another drug or device clinical investigation.
- 15. Subject with documented leukopenia (WBC < $3.5 \times 10^3/\mu$ L), acute anemia (Hgb < 10.0 gm/dL or < 6.2 mmol/L), thrombocytopenia (platelet count < 100x $10^3/m$ L), or history of bleeding diathesis or coagulopathy⁷.
- 16. Subject who requires a non-cardiac procedure such as carotid procedures or mediastinal tumor removal.

⁶ Previously implanted means that the EDWARDS INTUITY Aortic Valve implant procedure was completed. The EDWARDS INTUITY Aortic Valve procedure is complete when the surgeon takes the patient off cardiopulmonary bypass and restarts the heart.

⁷ WBC: White Blood Cells; Hgb: Hemoglobin

- 17. Subject had a stroke or transient ischemic attack within six months prior to scheduled aortic valve replacement surgery.
- 18. Study site pre-operative echocardiograpic assessment shows evidence of an intracardiac mass, thrombus, or vegetation.
- 19. Subject has hemodynamic or respiratory instability requiring inotropic support, mechanical circulatory support, or mechanical ventilation within 30 days of procedure.
- 20. Subject with documented renal insufficiency as determined by Serum creatinine ≥ 200 µmol/L (2.27 mg/dL) at screening or end-stage renal disease requiring chronic dialysis.
- 21. Subject with documented hyperparathyroidism.

6.3 INTRA-OPERATIVE CRITERIA

6.3.1 EXCLUSION CRITERIA

These exclusion criteria will be determined after subject consent, intraoperatively and before any attempt with an EDWARDS INTUITY valve is performed.

The Investigator may exclude any subject due to any of the following conditions:

- 1. Participation in the clinical investigation may be contrary to the subject's medical treatment;
- 2. Any anatomical findings that would not be suitable for implantation of the EDWARDS INTUITY Aortic Valve or use of the EDWARDS INTUITY Delivery System and which are discovered, intraoperatively. These may include findings such as:
 - a. Significant calcium on the anterior mitral leaflet which cannot be removed,
 - b. Septal hypertrophy that will not be corrected by myectomy, or pronounced septal calcification,
 - c. The position of the coronary ostia relative to the EDWARDS INTUITY Aortic Valve Models 8300ACA and/or 8300ACB would result in obstruction of blood flow,
 - d. Extensive calcification of the aortic root,
 - e. Left atrial thrombus,
 - f. the subject is hemodynamically unstable during the procedure requiring the procedure to be aborted prior to insertion of the investigational bioprosthesis and delivery system,
 - g. A device is not available in the correct size for the subject,
 - h. Annular deformation which may or may not be caused by too extensive decalcification of the aortic annulus;
- 3. It is discovered that the subject is participating in a clinical investigation of another drug or device prior to insertion of the investigational bioprosthesis and delivery system.

The Investigator will document the exclusion of investigation subjects and notify the Investigation Sponsor within 5 working days. Additional subjects will be screened to

replace those subjects who are excluded by the Investigator during the surgical procedure prior to implantation.

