6.4 WITHDRAWAL CRITERIA AND PROCEDURES

Subjects may voluntarily withdraw consent at any time during Phase I or Phase II of the clinical investigation with no loss of benefit or penalty. Subjects will be exempt from follow-up after withdrawing from the clinical investigation. For subjects who are consented but have withdrawn, the investigational center must retain the subject's informed consent and all documents pertaining to the subject prior to the subject's withdrawal. Additional subjects will not be enrolled to replace those subjects implanted with the bioprosthesis who chose to withdraw from the clinical investigation.

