9.3 SUBJECT ENROLLMENT

Subjects will be considered enrolled into the clinical investigation after meeting all the enrollment criteria, signing the informed consent, and after the surgeon sizes the aortic annulus, and determines that the bioprosthesis can be implanted. The point of enrollment in Phase I and Phase II of the clinical investigation is established in the Operating Room when the investigator sizes the aortic annulus and confirms that the subject is an appropriate candidate for the investigation device(s)¹⁰. All subjects enrolled in this clinical investigation must be followed as described in section 9.4 and section 9.5

Adverse events are collected from the time the subject provides consent.

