9.4.2 DISCHARGE

A clinical evaluation of Phase I or Phase II subjects, including an echocardiogram (refer to Section 9.5), will be performed at the time of hospital discharge. Medical information, findings, and results to be recorded are identified in Table 3.

¹⁰ The bioprosthesis and the delivery system must be used.

General information	Clinical information	Echocardiography ¹¹
Date of Discharge	Weight	Date of exam
	Heart rate	2D measurements
	Cardiac Rhythm (12-lead EKG)	Ejection fraction
	Anti-thromboembolic therapy	Aortic bioprosthesis assessment
	Adverse Events	LVOT assessment
	Coagulation Profile	Mitral Valve assessment
		Other Variables
		Left Ventricular Assessment

Table 3: Discharge Evaluation

Subjects, who are not discharged within 10 days post procedure must have an echocardiogram (refer to Section 9.5) to further assess placement and performance of the bioprosthesis. This echocardiogram is required to complete the evaluation of procedural success. Those subjects will not require an additional echocardiogram at discharge.

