9.8 INVESTIGATION SUBJECT EXIT

Investigation Subjects exit the investigation when no additional follow-up visits, procedures, or data collection are required. A subject is exited from the investigation in the following instances:

• Subject fails enrollment criteria after written consent (section 6)

TRITON Surgical Treatment of Aortic Stenosis with a Next Generation Surgical Aortic Valve Clinical Protocol Number: 2009-01

- Subject is excluded intra-operatively by investigator prior to attempted placement of the investigational device (section 6.3)
- Subject is Lost-to-follow-up (section 9.7)
- Subject withdraws from the investigation (section 6.3)
- Subject Death (section 11.3.1)
- Subject completes investigation follow-up (section 9.4.3

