12.4 PHASE II ANALYSIS

12.4.1 ANALYSIS POPULATION

The primary safety analysis will include all the enrolled subjects including those enrolled in Phase I. The performance analysis will include the subjects who survived at least 30 days post implant.

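### A subject enrolled at annulus sizing (9.3) can still be excluded, exited and replaced before the device attempt (6.3.1, 9.8), and subjects who never receive the valve have no defined place in the success rates (12.4.1)

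*Combined protocol and SAP*

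**What the plan says.** Section 9.3 of the combined protocol and SAP requires consent and all enrollment criteria, and says the point of enrollment is "established in the Operating Room when the investigator sizes the aortic annulus and confirms that the subject is an appropriate candidate". It then says that all enrolled subjects are to be followed under 9.4 and 9.5. Footnote 10, attached to the enrollment definition but printed under 9.4.2, adds: "The bioprosthesis and the delivery system must be used".

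Other sections set the limits for exclusion, exit and replacement:

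- **6.3.1, opening:** the intra-operative exclusions are determined "intraoperatively and before any attempt with an EDWARDS INTUITY valve is performed".
- **6.3.1, item 2f:** instability requiring the "procedure to be aborted prior to insertion of the investigational bioprosthesis and delivery system". Item 3 (participation in another investigation) uses the same moment.
- **6.3.1, closing sentence:** further subjects are screened to "replace those subjects who are excluded by the Investigator during the surgical procedure prior to implantation".
- **9.8, exit:** "Subject is excluded intra-operatively by investigator prior to attempted placement of the investigational device". There is no exception for a subject already enrolled.
- **6.4:** "Additional subjects will not be enrolled to replace those subjects implanted with the bioprosthesis who chose to withdraw".

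On analysis, 12.4.1 says: "The primary safety analysis will include all the enrolled subjects including those enrolled in Phase I". Its next sentence limits the performance analysis to subjects alive at least 30 days after implant. Section 5.2 defines device technical success as one valve delivered and deployed with one delivery system. Section 12.4.3 reports technical and procedure success as counts and percentages. Neither section names a denominator.

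**The concern.** Enrollment and the end of intra-operative exclusion should be the same moment, or exclusion should close first. Here enrollment comes first, so for part of the operation a subject is enrolled and can still be removed. The investigator makes that decision during surgery, and the 6.3.1 list of findings is open-ended.

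The study has a single arm, so the rates themselves are the evidence. Device technical success and procedure success describe whether the system can be delivered and deployed, and the subjects in whom it could not be are the informative failures. If such subjects can be replaced, or have no place in the denominator, the reported rates depend on how each of up to 8 Phase II centers reads the wording.

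**Working it through.** **1. Order of events.** By 9.3, sizing and confirmation of candidacy come before any attempt. In sequence the moments are: sizing and confirmation (9.3, enrollment); attempt or insertion (6.3.1 opening, items 2f and 3, and 9.8); implantation (6.3.1 replacement sentence). The nearest definition of the last is footnote 6, which treats *previously implanted* as procedure completed, with the subject off bypass and the heart restarted. That footnote serves a different criterion.

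**2. Subject A: sized and confirmed, then unstable before insertion.**

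| Provision | Consequence |
|---|---|
| 9.3 | enrolled, must be followed |
| 12.4.1 | in the primary safety analysis |
| 6.3.1 | may be excluded, and is replaced |
| 9.8 | exited, so no further follow-up |
| Footnote 10 | unclear: either a condition of enrollment or only an instruction to use both devices |

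The first two rows cannot be reconciled with the next two. Footnote 10 does not settle which applies.

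**3. Subject B: device attempted without success, another valve used.** The 6.3.1 opening and 9.8 close exclusion and exit at the attempt. Section 9.6 requires follow-up after device removal, and 9.6.1 includes excision before the procedure is completed. Section 12.4.1 keeps the enrolled subject in the safety analysis. Two gaps remain. The replacement sentence runs past the attempt to implantation, and 6.4 bars replacement only for implanted subjects who withdraw. Section 9.2.2 also sends a subject with a failed second attempt to another valve without stating follow-up or analysis status, and 9.6.1 does not clearly cover an attempt in which no valve was ever placed.

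**4. Denominator.** A performance population defined by survival after implant either excludes Subject B or leaves B undefined. Survival to 30 days is also unsuited to procedure success, which 5.2 settles at discharge or day 10 and for which death is a failure.

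**5. Size, by illustration.** Planned enrollment reproduces: 10 + 340 = 350. The documents give no number of intra-operative exclusions or failed attempts. Assume that k enrolled subjects never receive the valve and are left out of the denominator, that 350 others are reported, and that all 350 are technical successes. The reported rate is 350/350 = 100% (exact 95% CI 99.0% to 100%). With the k subjects counted as failures, the rate is 350/(350 + k):

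| k | Calculation | Rate | Exact 95% CI | Difference from 100% |
|---|---|---|---|---|
| 5 | 350/355 | 98.6% | 96.7% to 99.5% | 1.4 points |
| 10 | 350/360 | 97.2% | 95.0% to 98.7% | 2.8 points |
| 20 | 350/370 | 94.6% | 91.8% to 96.7% | 5.4 points |

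In each row the lower confidence limit of the reported 100% lies above the rate with everyone counted.

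**The case against.** A reader might infer that a subject whose device attempt failed can be exited, replaced and dropped from the safety analysis. The documents do not support that. Exclusion and exit both stop at the attempt, removal leads to follow-up under 9.6, adverse events are collected from consent (9.3), and the safety set is all enrolled subjects. The replacement sentence covers only subjects excluded by the investigator, so on a fair reading it inherits the earlier cut-off. This answer largely stands. What is left for the failed attempt is loose replacement wording and the undefined performance denominator.

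It can also be said that attempt, insertion and attempted placement are nearly the same moment, and that 9.3 requires all enrollment criteria to be met. The Synopsis lists the intra-operative criteria among the enrollment criteria, and 9.2.1 has the anatomy examined after aortotomy. Most anatomical exclusions should therefore be cleared before enrollment. That is fair and narrows the window. It does not close it: instability, or another finding arising between confirmation and attempt, still meets both sets of rules. Section 6.4 sets no exclusion boundary, and footnote 10 is ambiguous rather than contradictory.

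Finally, the illustration rests on an assumed k, and treating a subject in whom no device was opened as a device failure is debatable. Keeping never-implanted subjects in the denominator also dilutes early percentages for study-valve events such as thrombosis or paravalvular leakage. Both points stand. The statement about direction is therefore confined to the success rates, and subjects without an attempt should be listed separately.

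**Conclusion.** The conflict is real between sizing and the attempt: the same subject is enrolled and due follow-up under 9.3, and can be exited and replaced under 6.3.1 and 9.8. For a failed attempt the text protects follow-up and the safety analysis, but does not clearly bar replacement. The direct reason a never-implanted subject can fall out of technical and procedure success is the performance population in 12.4.1, together with the missing denominator. Leaving out failed attempts can only raise those rates.

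The size is unknown. The shift of 1.4 to 5.4 points assumes k of 5 to 20, no other technical failures, and every such subject left out. It is not an estimate for this study. No stated result is invalidated, but as written the success rates cannot be reproduced from the plan, so the wording should be changed.

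**What to change.** 1. Use the 9.3 enrollment point as the single boundary in 6.3.1, 9.3 and 9.8. In the 6.3.1 replacement sentence, change the limit from implantation to enrollment as defined in 9.3. State that no enrolled subject is exited as an intra-operative exclusion or replaced.
2. Reword footnote 10 so that it defines the attempted subset and is not a condition of enrollment.
3. In 12.4.1 and 12.4.3, state that device technical success and procedure success use all enrolled subjects in whom a device was attempted, with failed attempts counted as failures whatever the 30-day survival. List enrolled subjects without an attempt separately, and give an all-enrolled rate as a sensitivity analysis. Without this step, the first two changes would leave the performance population as it is.

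The cost is wording in five places, slightly lower reported success rates, and a few of the 350 who will not carry a study valve. Section 12.2 states its minimum numbers by valve size in implanted subjects, so those should be tracked by implant. The change concerns who is counted. The surgeon's choices and the clinical exclusion criteria stay as they are.

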6.4 WITHDRAWAL CRITERIA AND PROCEDURES

Subjects may voluntarily withdraw consent at any time during Phase I or Phase II of the clinical investigation with no loss of benefit or penalty. Subjects will be exempt from follow-up after withdrawing from the clinical investigation. For subjects who are consented but have withdrawn, the investigational center must retain the subject's informed consent and all documents pertaining to the subject prior to the subject's withdrawal. Additional subjects will not be enrolled to replace those subjects implanted with the bioprosthesis who chose to withdraw from the clinical investigation.

7 INVESTIGATIONAL DEVICE MANAGEMENT

7.1 DEVICE SHIPMENTS

An initial set of EDWARDS INTUITY Aortic Valves and EDWARDS INTUITY Delivery Systems will be shipped to the investigational center once the following conditions are met: the investigational center has obtained Ethics Committee approval, a signed Clinical Investigational Agreement is in place, and the Site Initiation Visit, including Principal Investigator training, has been completed. Additional devices will be sent to the investigational center as devices are used or as needed.

7.2 INVENTORY AND ACCOUNTABILITY RECORDS

All device shipments will have inventory and shipment records. Devices may be hand carried to participating investigational centers by Investigational Sponsor personnel and will be accompanied by delivery of investigational device documentation. The principal investigator(s) or designee will take inventory of the product and complete the delivery documentation with receipt date, condition of the device and signature. Both the investigational center and the Investigation Sponsor will retain copies of these documents.

The investigator will maintain a Device Accountability Log of all investigational devices received for use during this clinical investigation. The log will be kept with the documents for the clinical investigation and will be available for review during Investigational Sponsor monitoring visits. Documentation on the log will include:

- 1. Valve Model number
- 2. Valve serial number
- 3. Valve size
- 4. Delivery system Model number
- 5. Delivery system lot number
- 6. Delivery system size
- 7. Subject identification number for the clinical investigation, if device was used or opened

8. Date of use or if not used, date of return and Returned Goods Authorization (RGA) number (if applicable), or date of discard⁸.

7.3 DEVICE STORAGE

The device inventory will be stored in a locked, controlled, cool, dry and clean area as described in the Instructions for Use (IFU). This storage area shall be accessible only to the principal investigator(s), his/her co-investigator or approved designee. Only cardiac surgeons identified in the Clinical Investigational Agreement and the Delegation of Authority form on file at the Investigation Sponsor may use the investigational device.

7.4 DEVICE RETURN

The principal investigator(s) will be notified in writing upon termination of the clinical investigation. All unused devices in original package and/or those in opened packages as well as those removed from the original package will be returned upon receipt of this notice. The Investigator's copy of the Device Accountability log must document any unused devices that have been returned. In the event that the EDWARDS INTUITY Aortic Valve is removed from the package, the bioprosthesis should be placed in a container with a suitable histological fixative such as 10% formalin or 2% glutaraldehyde immediately and returned to the Investigation Sponsor. Refrigeration is not necessary under these circumstances. Contact Edwards the Investigation Sponsor for additional instructions.

8 TRAINING

8.1 TRAINING OF INVESTIGATIONAL CENTER PERSONNEL

Principal investigator(s) and support staff will be trained by the Investigation Sponsor on the use of the EDWARDS INTUITY Aortic Valve and the EDWARDS INTUITY Delivery System, the Protocol, the Clinical Investigator's Brochure, electronic Case Report Forms (eCRF) and Electronic Data Capture (EDC) system, device accountability procedures, GCP (Good Clinical Practices) Guidelines and other investigation documents as applicable. A "Delegation of Authority Form" will be completed at each investigational center designating which individuals are allowed to perform specific clinical investigation related tasks. The delegated tasks will determine what the training requirements are for each member of the investigation support staff.

8.2 DEVICES

Each cardiac surgeon participating in the clinical investigation must be trained on the use of the devices before screening potential subjects or using the EDWARDS INTUITY Aortic Valve and the EDWARDS INTUITY Delivery System.

